### 6.3.3. Sample Size

A total of approximately 558 mITT subjects will be randomized in a 1:1 fashion to MIRASOL:CONTROL. This sample size estimate accounts for 10% of subjects who are randomized but will never receive an on-study transfusion and thus, will not be included in the mITT analysis set and, therefore, the primary analysis. A total of 558 mITT subjects in MIRASOL versus CONTROL will provide approximately 85% power for establishing non-inferiority at the 1-tailed 0.025 level of significance (using a 2-sided 95% CI) accommodating a 10% relative increase in the mean rate of WHO grade 2 or higher bleeding (i.e.  $\mu_T / \mu_C = 1.1$ ).

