## 8.6. Interim Analysis

An IA will be conducted at the 50% information fraction, i.e. when approximately 279 randomized mITT subjects have completed the post-transfusion period follow-up/early termination visit. The results of the IA will be presented to the study's Data Monitoring Committee (DMC). The DMC will assess efficacy, safety, and quality of trial conduct at the time of the IA.

Empirical conditional power [4] will be used in the IA to assess the futility in establishing NI. This will be carried out as follows.

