A negative binomial model planned for the primary analysis will be fitted using unblinded data at the time of the IA following the convention for handling the off-protocol intervals prescribed in the primary analysis for each study arm. From these intercept only models, the estimates of  $\beta_0$  and the variance parameter  $\varphi$  will be obtained. For an individual to be recruited in the second half of the trial, this person's duration of time ( $t_i$ ) under observation will be drawn with replacement from each study arm's empirical distribution from the individuals who have completed their follow-up at the time of the IA regardless of on- or off-protocol intervals. The offset will be denoted as  $\ln(t_i)$ . Subjects whose time to transfusion independence is sampled and found to take place before Day 27 will be assumed to have zero bleeding days on the date of transfusion independence to Day 27 inclusive (which is assessed at the Post Transfusion follow-up visit). To simulate bleeding days over the period of transfusion dependence we first draw a random number  $V_i = \text{RAND}(\text{'GAMMA'}, 1/\varphi)$ , then compute  $U_i = V_i * \varphi$  such that  $U_i$  will be a gamma distributed with mean 1 and variance  $\varphi$ . The count response is then to be drawn from a Poisson distribution with mean  $U_i e^{\beta_0 + \ln(t_i)}$ . In order to simulate a count for the number of bleeding days which is guaranteed to be no greater than the number of bleeding assessment days for which bleeding data are required, a multinomial random variable will be generated with  $t_i + 1$  categories and probability vector  $P$  calculated based on the probability mass function of a right-truncated Poisson random variable. The resulting count will take on values 0, 1, 2, . . .,  $t_i$  while continuing to represent a realization of the bleeding data from the subject since it is using their estimated bleeding rate. When a cell probability for the multinomial is very small it will be set to  $1 \times 10^{-5}$  so that probabilities are  $> 0$  and to avoid computational errors caused by very small floating-point numbers. The count response drawn in this way will be a realization from the truncated negative binomial distribution.

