A completed dataset will then be available with the first half of the sample representing individuals for whom data are recorded and the second half of the sample representing simulated data representing contributions from individuals yet to be recruited. A negative binomial model will be fitted to this complete dataset as described for the primary analysis. A Wald-based two-sided 95% confidence interval will then be constructed for the regression coefficient of the treatment indicator based on this completed dataset. It will then be recorded whether the upper limit of this confidence interval includes the value of  $\ln 1.6$  which defines the non-inferiority margin on the scale of the natural logarithm.

Ten thousand datasets will be computed in this way and the proportion of completed datasets for which the upper limit of a two-sided 95% confidence interval is below the value of  $\ln 1.6$  will be taken as the empirical conditional power. If this empirical conditional power is below 0.30 the guidance would suggest termination for futility, but this would not be a binding rule. Factors other than the empirical conditional power will be considered when weighing the futility of the study as a whole.

The DMC will be fully unblinded in its assessment of safety and efficacy data at the time of the formal IA. The IA tables will be prepared semi-blinded by treatment codes (e.g. Treatment A and Treatment B) and the actual treatment assignments will be provided to the DMC under separate cover.

Note that the power calculation does not consider the minor power loss due to the futility analysis. The study will not be stopped at the IA for a positive primary efficacy outcome (e.g. non-inferiority or superiority of MIRASOL).

The DMC will receive their routine unblinded DMC report at the IA. In addition, the following data will be included in the IA report:

A summary of the mean, SD, minimum and maximum days of grade 2 or higher bleeding and days of bleeding assessments will be included by treatment group alone and by treatment group and treatment type.

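### The SAP calls the power loss from its futility rule minor; if the 0.30 guidance is always followed, power at the planned ratio of 1.1 is about 77%, not 85%

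*SAP*

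**What the plan says.** Section 6.3.3 of the SAP says that 558 mITT subjects "will provide approximately 85% power for establishing non-inferiority at the 1-tailed 0.025 level of significance", "accommodating a 10% relative increase in the mean rate of WHO grade 2 or higher bleeding", that is, at a true rate ratio of 1.1. Section 8.1.3 sets the non-inferiority margin at 1.6. The power statement carries no qualifier about the interim look.

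Section 8.6 sets the timing: "An IA will be conducted at the 50% information fraction", about 279 mITT subjects. Negative binomial models fitted to the unblinded interim data follow the off-protocol convention "prescribed in the primary analysis for each study arm. From these intercept only models, the estimates of" the intercept and the dispersion are obtained, and these are used to simulate the subjects not yet recruited. The empirical conditional power is the share of 10,000 completed datasets whose upper confidence limit lies below ln 1.6.

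The section then says: "If this empirical conditional power is below 0.30 the guidance would suggest termination for futility, but this would not be a binding rule". It adds: "Factors other than the empirical conditional power will be considered when weighing the futility of the study as a whole". Stopping for success at the interim is excluded. On the cost of the look it says only: "Note that the power calculation does not consider the minor power loss due to the futility analysis".

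**The concern.** The SAP is open that the 85% ignores the futility look. The problem is the adjective: it describes a size, no figure supports it, and the rule as written does not have that property if it is followed.

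Conditional power computed from interim estimates (the current trend) reacts strongly to chance at half information. A trial with a true ratio of 1.1 can easily show an interim ratio above 1.3, and the rule then projects that unlucky estimate onto the second half. No early stop for success is allowed, so nothing is gained back at the interim.

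A non-binding recommendation has to be weighed, and for that the DMC needs to know how often the rule would stop a trial that deserves to continue. The interim report contents in section 8.6 include the estimate, its standard error, the 95% CI and the margin, but not the rule's error rates.

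**Working it through.** **Inputs from the SAP.** One-sided alpha 0.025, power 85%, true ratio 1.1 and 558 mITT subjects (6.3.3); margin 1.6 (8.1.3); information fraction 0.5 and conditional power cut 0.30 on interim estimates (8.6). The 85% cannot be rebuilt, because the documents give neither a control bleeding rate nor a dispersion. It is taken as stated. The analytic steps below need neither quantity.

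**1. Standard error implied by the stated power.**
SE = [ln(1.6) − ln(1.1)] / (1.960 + 1.036) = 0.3747 / 2.996 = 0.1250. At half information, SE = 0.1250 × √2 = 0.1768.

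**2. Stopping boundary.** Let z1 be the interim Z statistic against the margin. Current-trend conditional power is
CP = Φ[(z1/√0.5 − 1.960)/√0.5].
Setting CP = 0.30 gives z1 = √0.5 × (1.960 − 0.524 × √0.5) = 1.124. As a ratio: 1.6 × exp(−1.124 × 0.1768) = 1.312. For comparison, the largest final estimate that still succeeds is 1.6 × exp(−1.960 × 0.1250) = 1.252.

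**3. Behaviour at a true ratio of 1.1.** z1 is normal with mean 2.996 × √0.5 = 2.119 and variance 1.
- P(stop) = Φ(1.124 − 2.119) = 0.160.
- P(z1 ≥ 1.124 and final Z > 1.960), bivariate normal with correlation √0.5, = 0.772.
- Loss = 0.850 − 0.772 = 0.078 (0.0776 unrounded).
- Share of stopped trials that would have succeeded: 0.0776 / 0.160 = 49%.
- Share of otherwise successful trials ended: 0.0776 / 0.850 = 9.1%, about one in eleven.
- Half of the stop recommendations acted on: 0.850 − 0.5 × 0.0776 = 0.811.
- Sample size with the same power and no look: 558 × [(1.960 + 0.747)/(1.960 + 1.036)]² ≈ 455.

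**4. Other true ratios, guidance always followed.**

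| True ratio | P(stop) | P(non-inferiority), no look | P(non-inferiority), rule followed |
|---|---|---|---|
| 1.0 | 6.3% | 96.4% | 92.0% |
| 1.1 | 16.0% | 85.0% | 77.2% |
| 1.2 | 30.8% | 63.3% | 54.7% |
| 1.6 | 86.9% | 2.5% | 1.9% |

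**5. Sensitivity at ratio 1.1.** Planned power of 84% to 86% gives 76.1% to 78.4% with the rule followed. An information fraction of 0.45 to 0.55 gives 76.1% to 78.2%.

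**6. Simulation of the section 8.6 procedure at ratio 1.1.** Control mean and dispersion are assumed, in pairs consistent with the stated 85%. Two separate programs were run.

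| Program | Control mean (days) | Dispersion | P(stop) | Power, no look | Power, rule followed |
|---|---|---|---|---|---|
| A | 1 | 1.23 | 13.6% | 87.7% | 80.3% |
| A | 2 | 1.70 | 15.6% | 85.8% | 77.1% |
| A | 3 | 1.86 | 14.1% | 86.0% | 79.5% |
| B | 1 | 1.23 | 16.5% | 85.3% | 77.0% |
| B | 2 | 1.70 | 14.0% | 85.5% | 78.7% |

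Program A used 2,000 to 2,500 trials with 100 completions each; program B used 1,500 trials with 300 completions each. The losses run from about 6.5 to 8.7 points, with Monte Carlo error of roughly 0.6 point on a loss in program A and about 1 point on each power in program B. Both programs fixed 28 assessed days for every subject and had no off-protocol intervals. They support the approximation but do not test those features.

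**7. When the adjective would fit.** If conditional power were computed under the design ratio of 1.1 instead of the interim trend, power with the same 0.30 cut would be 84.5%, a loss of 0.5 point. Section 8.6 does not describe that calculation. At the actual boundary, conditional power under a ratio of 1.1 is Φ[(0.795 + 0.5 × 2.996 − 1.960)/√0.5] = 68%, where 0.795 = 1.124 × √0.5, while the rule reports 30%.

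**The case against.** The strongest reply is that mandatory stopping is not the rule. The guidance is non-binding, other factors are weighed, and the DMC also sees the estimate and its interval. The loss could therefore be anywhere from 0 upward: 3.9 points at half adherence, and about 8 only if the guidance is always followed. The documents set no threshold for a minor loss, and no number in the SAP is contradicted, because the 85% is expressly stated without the look. This stands as a limit on the size: 77% is a full-adherence figure and must be labelled as such. It does not rescue the adjective, because the text offers no adherence assumption under which the loss would be small.

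A second reply is that the Clinical Investigation Plan (CIP) or a DMC charter may give the operating characteristics. Neither is in view; the file supplied as the protocol carries the same SAP text. So the absence of a figure is established only for the documents at hand.

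A third is that the simulations are simplified and some give 79% to 80% with the rule followed. That is fair, and it is why the sponsor should confirm the figure with its own planning mean and dispersion. The loss was of similar size in every setting tried.

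**Conclusion.** The concern holds. Following the 0.30 guidance costs about 8 points of power at the planned ratio, 85.0% to 77.2% by normal approximation; the actual loss lies between 0 and that, depending on how often the DMC acts on it. The result rests on the stated 85%, ratio 1.1, margin 1.6, information fraction 0.5, and the reading of section 8.6 as conditional power on the interim trend. Type I error is not inflated: it falls from 2.5% to 1.9% if the rule is followed. The weakness is one of description and missing operating characteristics, and should be fixed. It does not threaten the validity of the final test.

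**What to change.** In section 8.6, delete the word and state the cost. Suggested text: *The 85% power in section 6.3.3 applies if the futility guidance is not acted on. If every empirical conditional power below 0.30 led to termination, power at a true ratio of 1.1 would be about 77%.* The sponsor should confirm or replace the 77% by simulation with its own planning mean and dispersion. Add the same qualifier to section 6.3.3.

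Give the DMC a small table of stopping probabilities and power with and without the rule: stopping in about 6% of trials at ratio 1.0, 16% at 1.1, 31% at 1.2 and 87% at 1.6, again subject to the sponsor's confirmation. If the CIP already quantifies the loss, cite that figure in section 8.6.

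The cost is wording in two sections and one table. The rule, the 0.30 cut, the sample size, the data and the final test do not change. The only drawback is that the stated power with the guidance followed looks less favourable.

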## 10. APPENDIX I, ANNOTATED WHO GRADING SCALE

WHO Grading Scale for Bleeding annotated with the study's Bleeding Assessment (MIPLATE Annotated eCRFs) variable identifiers (Bx) and answers that correspond to the bleeding status.

	Grade 1	Grade 2	Grade 3
Oral and nasal	
 
Oropharyngeal bleeding – total duration of all episodes in previous 24 hours <math>\leq</math> 30 minutes* B6a = No
 
Petechiae of oral mucosa B5 = Yes
 
Epistaxis – total duration of all episodes in previous 24 hours <math>\leq</math> 30 minutes* B7a = No
 
	
 
Oropharyngeal bleeding – total duration of all episodes in previous 24 hours <math>></math> 30 minutes* B6a = Yes or Not Assessed or Refused or Don't Know
 
Epistaxis – total duration of all episodes in previous 24 hours <math>></math> 30 minutes* B7a = Yes or Not Assessed or Refused or Don't Know
 
	
 
Any bleeding requiring RBC transfusion over routine transfusion needs** B8 = Yes
 

Skin, soft tissue, musculoskeletal	
 
Petechiae of skin B9 = Yes
 
Purpura <math>\leq</math> 1-inch diameter B10a = No
 
One or more spontaneous hematomas in the soft tissue or muscle <math>></math> 1 inch B11 = Yes
 
	
 
Purpura <math>></math> 1-inch diameter B10a = Yes or Not Assessed or Refused or Don't Know
 
Spontaneous hematoma in deeper tissues B12 = Yes
 
Joint bleeding (confirmed by aspiration, imaging study or other accepted technique) B13 = Yes
 
	
 
Any bleeding requiring RBC transfusion over routine transfusion needs** B14 = Yes
 

Gastrointestinal	
 
Positive stool occult blood test B15a = Yes
 
	
 
Melanotic stool B16 = Yes
 
Hematochezia – visible red blood mixed in stool, not requiring a transfusion B17 = Yes
 
Hematemesis – Grossly visible blood in emesis or in nasogastric drainage tube (not related or secondary to swallowed blood) B18a = Yes or B19a = Yes
 
	
 
Any bleeding requiring RBC transfusion over routine transfusion needs** B20 = Yes
 

Genitourinary	
 
Any biochemical or microscopic Hb/RBCs without red urine B21a = Yes
 
Abnormal vaginal bleeding (Unexpected bleeding out of normal cycle OR Bleeding heavier than normal OR Breakthrough bleeding (patient on hormonal therapy to prevent bleeding)) with spotting B23a = Yes
 
	
 
Gross/visible hematuria without need for transfusion B22 = Yes
 
Abnormal vaginal bleeding (Unexpected bleeding out of normal cycle OR Bleeding heavier than normal OR Breakthrough bleeding (patient on hormonal therapy to prevent bleeding)) more than spotting B23b = Yes
 
	
 
Any bleeding requiring RBC transfusion over routine transfusion needs** B24 = Yes
 

Pulmonary		
 
Hemoptysis – Visible blood B25 = Yes
 
Blood in broncho-pulmonary lavage, or blood tinged sputum (excluding those with nose or oropharyngeal bleeding) B26a = Yes or B27 = Yes
 
	
 
Any bleeding requiring RBC transfusion over routine transfusion needs** B28 = Yes
 

Body Cavity		
 
Visible blood in body cavity fluid (eg red cells apparent in fluid aspirate) short of criteria for grade 3 or 4 B29a = Yes
 
	
 
Grossly bloody body cavity fluids and organ dysfunction with symptoms, and/or need to intervene (e.g. to aspirate), and/or need for transfusion B30 = Yes
 

Central Nervous System (CNS)		
 
• Retinal bleeding without visual impairment B31a = Yes
 
• Lumbar puncture with blood (> 5 RBC/ <math>\mu</math>L in CSF on microscopic analysis and non-traumatic tap), no symptoms and no visible red color B32a = Yes
 
	
 
• Lumbar puncture with visible red color in absence of symptoms, and non-traumatic tap B32b = Yes
 

Invasive Sites		
 
• Bleeding at invasive sites (venipuncture sites, IV lines or catheter exit sites): active oozing at site for a cumulative total of > 1 hour in the previous 24 hours B34 = Yes
 
	
 
• Any bleeding requiring RBC transfusion over routine transfusion needs** B35 = Yes
 

Hemodynamic Instability			
 
• Any bleeding associated with moderate hemodynamic instability (hypotension; > 30mmHg fall or > 30% decrease in either systolic or diastolic BP) and requiring RBC transfusion over routine transfusion needs** B37 = Yes
 

Abbreviations: RBC = red blood cell, Hg = hemoglobin, CSF = cerebrospinal fluid, IV = intravenous, mmHg = millimeters of mercury, BP = blood pressure.

\*Count actual bleeding (ie. “running out” or need for basin, Kleenex, towel, etc.) not minor bleeding.

\*\*Red cell transfusion must be specifically related to treatment of bleeding within 24 hours of onset of bleeding.

**Grade 4:**

- Any bleeding associated with severe hemodynamic instability (hypotension; > 50mm/Hg fall or > 50% decrease in either systolic or diastolic BP, with associated tachycardia (HR increase of  $\geq$  20% for 20 minutes) and requiring RBC transfusion over routine transfusion needs **B36 = Yes**
- Fatal bleeding from any source **B38 = Yes**
- Retinal bleeding with visual impairment (visual impairment is defined as a field deficit, and patients with suspected visual impairment require an ophthalmologic consult for

- documentation) **B31b = Yes**
- Central nervous system (CNS) symptoms with non-traumatic bloody lumbar puncture **B32c = Yes**
- CNS bleeding on imaging study with or without dysfunction **B33a = Yes**

Grade 4 = (B31b=Yes or B32c=Yes or B33a=Yes or B36=Yes or B38=Yes)

Grade 3 = (B8=Yes or B14 or B20=Yes or B24=Yes or B28=Yes or B30=Yes or B32b=Yes or B35=Yes or B37=Yes)

Grade 2 = (B6a=Yes or Not Assessed or Refused or Don't know or B7a=Yes or Not Assessed or Refused or Don't Know or B10a=Yes or Not Assessed or Refused or Don't know or B12=Yes or B13=Yes or B16=Yes or B17=Yes or B18a=Yes or B19a=Yes or B22=yes or B23b=Yes or B25=Yes or B26a=Yes or B27=Yes or B29a=Yes or B31a=Yes or B32a=Yes or B34=Yes)

Grade 1 = (B6a=No or B5=Yes or B7a=No or B9=Yes or B10a=No or B11=Yes or B15a=Yes or B21a=Yes or B23a=Yes)

The maximum grade in the 24-hour assessment period will be the bleeding grade for that day

## 11. APPENDIX II, ANALYSIS OF THE KEY SECONDARY ENDPOINT

### 11.1. Introduction

Alloimmunization against the highly polymorphic human leukocyte antigens (HLA) has long been known to occur in oncology patients receiving platelet transfusions.[1,2] A major concern with HLA alloimmunization is the risk of HLA antibody formation contributing to platelet refractoriness, though it is known that alloimmunization is only one of many causes of platelet transfusion refractoriness.[3] The majority of HLA alloimmunization events following transfusion of oncology patients occurs within the first four weeks of induction chemotherapy.[2,4] Animal models show decreased alloimmunization in recipients of ultraviolet (UV) light treated platelets.[5,6] A definitive randomized control trial showed clear benefit of leukoreduction or UVB irradiation of platelet products in preventing both HLA alloimmunization and refractoriness to platelet transfusion.[4] The primary objective of MIPLATE is to determine if the hemostatic efficacy of Mirasol-treated plasma stored Trima Accel® apheresis platelets are non-inferior to conventional plasma stored apheresis platelets in patients with hypoproliferative thrombocytopenia requiring platelet transfusions. Secondary objectives include comparing other efficacy and safety endpoints between the treatment groups. One of the key secondary endpoints in the MIPLATE trial is to determine if receipt of Mirasol-treated platelets alter the risk for HLA alloimmunization after platelet transfusion.

### 11.2. Data Sources

Data and specimens from the enrolled patients in MIPLATE will be accessed for this assessment of alloimmunization.

Samples from enrolled patients will be screened for Class I and Class II antibodies at BSRI using the LSM12 kit manufactured by One Lambda. Samples will be tested at baseline (pre-transfusion) and on days 14 ( $\pm$  5 days), 28 ( $\pm$  7), and 56 ( $\pm$  10 days). Blood System Research Institute laboratory staff will be blinded to MIPLATE treatment assignment.

### 11.3. HLA Antibody Testing

Test results will be reported as the normalized background (NBG) ratio for each bead in the assay, which corresponds to the strength of each HLA reaction. The NBG ratio and assay validity are calculated using the following set of abbreviations:

S#N	Sample-specific fluorescent value for bead #N
SNC bead	Sample-specific fluorescent value for Negative Control bead
SPC bead	Sample-specific fluorescent value for Positive Control bead
BG#N	Background NC Serum fluorescent value for bead #N
BGNC bead	Background NC Serum fluorescent value for Negative Control bead
NC Serum	Negative Control Serum validated for a given lot of LABScreen ® beads

For an assay to be interpreted as valid, the following criteria will need to be met:  $SNC \leq 1500$ ,  $SPC \geq 500$ , and  $SPC \geq 2*(SNC)$ .

The NBG value for each bead will be calculated as:

$$NBG = (S\#N - SNC \text{ bead}) / (BG\#N - BGNC \text{ bead})$$

If any bead for a given sample yields an NBG ratio greater than the chosen cut-off the MIRASOL will be interpreted as positive, meaning evidence of alloimmunization. Cutoffs will be analyzed using a sensitive cutoff originally suggested by the manufacturer (NBG = 2.2) and cutoffs determined through studies of non-transfused males, using 3X or 5X the standard deviation above the mean value in that population.[7]

## **11.4. Analysis Objectives**

The objective of the study is to compare the rate of HLA alloimmunization for recipients of Mirasol-treated platelets and recipients of conventional platelets. The treatment effect will be measured by the odds ratio (OR). The relative odds of alloimmunization (comparing Mirasol-treated to conventional platelets) will be estimated at each of the three assay cutoffs, along with associated 95% confidence intervals. In addition, HLA antibody data will be examined using KM plots to explore time to alloimmunization, with the outcome of interest being time to development of new HLA antibodies. Individuals not experiencing alloimmunization will have their follow-up censored. All analyses will be conducted both as intention to treat analysis and a per protocol analysis.

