## **11.6. Endpoints and Covariates**

The endpoint for the HLA alloimmunization study will be development at any post-transfusion time point of a positive HLA antibody test at the given assay cutoff in a subject who had a negative HLA antibody test at that assay cutoff at baseline (pre-transfusion).

A relevant covariate that will be analyzed in a secondary analysis is the number of platelet transfusions received prior to the alloimmunization event, which will allow calculation of the rate of alloimmunization per unit of platelets transfused.

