## **11.8. Statistical Procedures**

Odds ratios will be calculated to compare the risk of HLA alloimmunization in recipients of Mirasol-treated vs. conventional platelets. The exposure will be platelet type and the outcome will be development of a new HLA antibody. Development of HLA class I and HLA class II antibodies will be analyzed separately. The number of participants in each group at risk for alloimmunization will depend on the intention to treat and per protocol final categorization, but in general will be the number of participants who did not have detectable HLA antibodies at baseline at a given assay threshold.

In secondary analyses KM curves will be calculated using the longitudinal HLA antibody data to define subjects who are alloimmunized at baseline and the time to development of HLA alloantibodies post-transfusion. Development of HLA alloantibodies will be considered “failure” events during model specification, and the two arms of the study will be compared statistically using standard non-parametric tests, such as the log-rank test, with a p-value less than or equal to 0.05 considered evidence for significant difference

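### Time to HLA alloimmunization is interval-censored by the sampling schedule, but Appendix II plans ordinary Kaplan-Meier curves and a log-rank-type test with no rule for dating events or censoring

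*SAP*

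**What the plan says.** The key secondary endpoint is analysed under SAP Appendix II. Section 11.2 sets the schedule: "Samples will be tested at baseline (pre-transfusion) and on days 14" (±5), 28 (±7) and 56 (±10). Section 11.6 defines the event, in subjects negative at baseline, as "development at any post-transfusion time point of a positive HLA antibody test at the given assay cutoff". It gives no date of conversion.

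Section 11.4 measures the treatment effect by the odds ratio and adds that "HLA antibody data will be examined using KM plots to explore time to alloimmunization". On censoring it says only: "Individuals not experiencing alloimmunization will have their follow-up censored". Section 11.8 places the curves among the secondary analyses ("In secondary analyses KM curves will be calculated using the longitudinal HLA antibody data") and adds that "the two arms of the study will be compared statistically using standard non-parametric tests, such as the log-rank test", with p ≤ 0.05 read as evidence of a difference.

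Interval censoring is not mentioned anywhere in Appendix II. Section 7.8 of the main SAP says that visits go by their database labels and that no windows are derived. It does not say whether this governs the laboratory's analysis in Appendix II.

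**The concern.** Kaplan-Meier and the log-rank test take each event time as known. Here an antibody first seen in one sample may have formed at any time since the previous negative one, with nominal gaps of 14, 14 and 28 days. Someone must therefore choose a date, and the plan does not say which. The first positive sample is the usual choice. It can only place conversion at or after its true time, so the curve partly traces the blood-draw schedule. With no sample missed, the longest possible delay is 66 − 21 = 45 days (negative on Day 21, positive on Day 66).

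At stake is how the curve reads, above all around Day 28. The permitted Day 28 samples run from Day 21 to Day 35, so about half of them may come after the day at which a reader would naturally read off a four-week risk.

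**Working it through.** The documents state no delay, four-week risk or event count for this analysis, so there is no figure of the plan's own to reproduce.

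**Inputs from SAP 11.2.** Sample windows are Days 9-19, 21-35 and 46-66.

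**Assumptions, since the documents are silent.** Events are dated at the first positive sample and nobody drops out, so Kaplan-Meier equals the observed cumulative proportion. Of the converters, 70% convert by Day 28, evenly from an onset day *a* to Day 28, and 30% convert evenly over Days 28-56. The onset *a* is set to 0, 5 or 7. The relative error does not depend on how many subjects convert.

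**Mean delay.** On nominal days, with conversion even over Days 0-56, it is (14×7 + 14×7 + 28×14)/56 = 10.5 days. With 70% converting by Day 28 from Day 0 it is 0.7×7 + 0.3×14 = 9.1 days; with 90% it is 0.9×7 + 0.1×14 = 7.7 days. Simulation over other conversion curves and spreads of sample dates gave 7.7 to 13.2 days. With 20% of the Day 14 and Day 28 samples missing, it was about 12 to 14 days.

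**Day 28 value, all samples on nominal days.** Everyone who converts by Day 28 is positive by the Day 28 sample, so the error is 0%.

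**Day 28 value, actual dates uniform over the windows.** The Day 14 sample has mean day 14. Half of the Day 28 samples fall by Day 28, with mean day 24.5. The share of conversions recorded by Day 28 is

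[0.5(24.5 − a) + 0.5(14 − a)]/(28 − a) = (19.25 − a)/(28 − a).

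- a = 0: 19.25/28 = 0.688, 31% too low
- a = 5: 14.25/23 = 0.620, 38% too low
- a = 7: 12.25/21 = 0.583, 42% too low

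For example, if 25% convert in all, the true Day 28 risk is 0.25 × 0.70 = 17.5%. With a = 5 the curve shows 17.5% × 0.620 = 10.8%.

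**Day 28 value, visit labels.** A Day 28 sample taken early misses 0.5×3.5 = 1.75 days of conversions on average. One taken late picks up 1.75 days of later ones. The net relative loss is 1.75/(28 − a) − (0.30×1.75/28)/0.70 = 1.75/(28 − a) − 0.027, which is 4%, 5% and 6% for a = 0, 5 and 7. Systematic sampling at a window edge would move this. With 75% converting by Day 28 from Day 0, all samples at the early edge give 1 − 21/28 = 25% too low. All at the late edge give (0.75 + 0.25×7/28)/0.75 = 1.083, or 8% too high.

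**With 20% of the Day 14 and Day 28 samples missing independently.**

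- Nominal days, a = 0: 0.5×0.96 + 0.5×0.80 = 0.88, 12% too low. Across nominal days and labels the range is 12-19%.
- Actual dates: [0.4(24.5 − a) + 0.6×0.8(14 − a)]/(28 − a). This is 16.52/28 = 0.590 for a = 0 (41% too low) and 10.36/21 = 0.493 for a = 7 (51% too low).

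**Comparison between arms.** In simulation with no true difference, log-rank size stayed at 4.5% to 8%, even with 10% of Day 28 samples missing in one arm and 50% in the other.

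**Alternative estimator.** In simulation the Turnbull estimate at Day 28 was 0.165-0.173 against true values of 0.170-0.179, within about 1 percentage point.

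**The case against.** The strongest reply is that the plan reports no Day 28 risk. The curves are exploratory, no four-week landmark is named, and SAP 7.4 treats key secondary outcomes as supportive and exploratory. The odds ratio (11.4) and Fisher's exact test (8.2.1) need no dates. Both arms share one schedule, and laboratory staff are blinded. Section 11.8 offers the log-rank test only as an example. All of this stands, and it limits how much the point matters.

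It is also fair to say that the size turns on conventions that the SAP leaves open. Appendix II is part of the SAP, and if the visit-label rule of 7.8 applies, most of the Day 28 error goes. Reading the curve at Day 35, when the window closes, also shrinks it. With 25% converting and onset at Day 5, the curve there shows 0.166, against a true Day 28 risk of 0.175 (5% lower) and a true Day 35 risk of 0.194 (14% lower).

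A reader might therefore infer that the plan understates four-week risk by about a third. The documents do not support that as a fact. It needs first-positive dating, actual sample dates spread across the windows and an assumed conversion curve, and none of these is stated. Nor does 11.1 settle the timing. Its statement that "The majority of HLA alloimmunization events following transfusion of oncology patients occurs within the first four weeks of induction chemotherapy" runs on the induction-chemotherapy clock, whereas study days run from the first study transfusion and the population includes transplant patients.

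The reply does not remove the average delay of more than a week, which is present at nominal visits too. Nor does it supply the missing dating rule.

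**Conclusion.** The point holds as a low-priority improvement. The data are interval-censored by design, the planned estimator treats event times as exact, and neither event nor censoring dates are defined. Under first-positive dating, conversion appears about 8 to 14 days late on average, the upper part of that range mainly reflecting missed interim samples. The Day 28 value is 0% too low on nominal days, about 4-6% with visit labels, and about 30-40% with actual dates spread uniformly over the windows. With 20% of interim samples missing it is 12-19% for nominal days or labels and 41-51% for actual dates. These figures assume the conversion curves above and no dropout.

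A reader might go further and conclude that the key secondary result or the between-arm test is unsound. That does not follow. The main comparisons use no dates, and the log-rank test is little affected when both arms follow the same schedule. Sampling that differs by arm is possible, but nothing in the documents suggests it. The gain is in the secondary descriptive curve.

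**What to change.** In SAP 11.4 and 11.8:

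- Estimate time to alloimmunization with the interval-censored (Turnbull) estimator.
- Give each converter the interval (last negative sample date, first positive sample date].
- Right-censor the others at their last negative sample date.
- Name the generalized log-rank test as the companion test.
- Use actual sample dates, and say so, so that it is clear whether 7.8 applies.

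PROC ICLIFETEST does this in SAS 9.4, the software already named in 11.10.

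The cost is SAP wording and a different procedure on the same data. The downside is that the curve is undefined within some intervals and is drawn with gaps there. If the sponsor keeps Kaplan-Meier, the least change is to state the event and censoring dates and to report cumulative proportions by scheduled visit.
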